12.4.3 Handling of missing values/censoring/discontinuations

Subjects who discontinue between Week 4 and Week 16, will be required to complete the End-of-study Visit assessments as shown in [Table 8-1](#). The plaque status based on the TCS at the End-of-study Visit will be used for the primary endpoint assessment i.e., the last observation carried forward approach will be applied. Subjects discontinued before Week 4 will be treated as failures.

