Subjects should be seen for all visits/assessments as outlined in the assessment schedule or as close to the designated day/time as possible. Missed or rescheduled visits should not lead to automatic discontinuation. Subjects who prematurely discontinue the study for any reason should be scheduled for a visit as soon as possible, at which time all of the assessments listed for the final visit will be performed. At this final visit, all dispensed investigational product should be reconciled, and the AEs and concomitant medications recorded on the eCRF.

[REDACTED]

Table 8-1 Assessment schedule

Visit name	Screening	Baseline	End of study	Unscheduled
Visit number	1	2	3	-
Week	-4 to -1	-	16	-
Day	-28 to -1	1	112	-
Informed consent	X			
Inclusion/exclusion criteria	X	X		
Pregnancy test ²	X	X		
Randomization via NIRT		X		
Physical examination	X	X	X	X
Smoking history	X			
Medical history	X			
Relevant family history	X			
Demography	X			
Psoriasis medical and treatment history	X			
QFT	X			
Skin type	X			
Body temperature (°C)	X	X		
Height (cm)	X			
Weight (Kg)	X	X	X	
Vital signs	X	X	X	
Electrocardiogram	X			
Laboratory assessments	X		X	
Adverse events ³	X	X	X	X
Drug administration record		X	X	X
Concomitant medications	X	X	X	X
TCS of target plaque	X	X	X	X
Skin biopsies ██████████ ⁶		X	X	
Information on study completion			X	

Baseline Visit (Visit 2) should be conducted within 28 days of the Screening Visit (Visit 1).

Unscheduled visits can be decided by the Investigators according to their own clinical judgment and practice.

End-of-study assessments (Visit 3) should be conducted only on subjects who complete 4 to 16 weeks of treatment. There will be a \pm 2-day window for Visit 3 (Week 16)

- [REDACTED]
- 2) Performed on serum for women of childbearing potential
 - 3) SAEs collected up to 30 days after the last administration of study treatment

[REDACTED]

6) At Baseline, two 6-mm punch biopsies will be taken, one from the identified active plaque (TCS \geq 6) and one from never-lesional skin. At the End-of-study Visit, one biopsy will be taken from the same area of the plaque sampled at Baseline. Biopsies should be sampled from the trunk whenever possible to avoid scars in exposed areas of the body

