12.4 Analysis of the primary endpoint

12.4.1 Definition of primary endpoint

The primary objective is to assess the superiority of secukinumab over guselkumab in controlling clinical activity in psoriatic plaques resistant to treatment with ustekinumab.

The primary endpoint is the proportion of subjects whose plaque achieves “clear” or “almost clear” status (TCS = 0-2) by 16 weeks of treatment with secukinumab or guselkumab.

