12.4.2 Statistical model, hypothesis, and method of analysis

The number (%) of subjects whose plaques achieve “clear” or “almost clear” status (TCS = 0-2) at Week 16 (i.e., responders) will be provided based on the FAS together with the 95% confidence interval using the exact method for the difference in proportions of responders in each arm.

Furthermore, a 1-sided Fisher’s exact test for the difference in the proportions of responders in the secukinumab (P1) and gesulkumab (P2) arms, $H_0: P_1 - P_2 = 0$ versus $H_1: P_1 - P_2 > 0$ at a Type I error rate of 0.05 will be performed.

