12.4.4 Sensitivity and supportive analyses

Analysis of the primary endpoint as observed i.e., without missing data imputation (as described in [Section 12.4.3](#)) will be performed as a sensitivity analysis for the primary endpoint.

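### A plaque cleared by a prohibited psoriasis treatment can count as a response to the assigned drug in subjects who discontinue at Week 4 or later

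*Protocol*

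**What the plan says.** Section 12.4.1 defines the primary endpoint as a clear or almost clear plaque (TCS 0-2) "by 16 weeks of treatment with secukinumab or guselkumab". Section 12.4.2 counts responders by "status (TCS = 0-2) at Week 16 (i.e., responders) will be provided based on the FAS".

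Section 12.4.3 sets the rule for early stoppers. "Subjects who discontinue between Week 4 and Week 16, will be required to complete the End-of-study Visit assessments", and then "The plaque status based on the TCS at the End-of-study Visit will be used for the primary endpoint assessment"; the same sentence describes this as last observation carried forward. Also, "Subjects discontinued before Week 4 will be treated as failures". Other treatment is not mentioned.

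Two provisions govern when the End-of-study TCS is taken:

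- Section 8, for subjects who leave the study: "Subjects who prematurely discontinue the study for any reason should be scheduled for a visit as soon as possible". The notes to Table 8-1 add that End-of-study assessments "should be conducted only on subjects who complete 4 to 16 weeks of treatment".
- Section 9.1.1, for subjects who stop study drug: they are not withdrawn unless they withdraw consent, and where possible they return according to the assessment schedule. The only scheduled visit after Baseline in Table 8-1 is Week 16.

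Section 6.2.2 bars systemic psoriasis treatments, phototherapy and active topicals during the study, except mild topicals on the face, scalp or genitoanal area. Section 9.1.1 lists prohibited treatment among the reasons to stop study drug, subject to the recommendations in 6.2.2. The only sensitivity analysis, in Section 12.4.4, is "Analysis of the primary endpoint as observed i.e., without missing data imputation", with a reference back to 12.4.3.

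**The concern.** The endpoint is worded as clearance on the assigned drug, and the trial compares two mechanisms, direct IL-17A blockade and IL-23p19 blockade. A plaque cleared by methotrexate, phototherapy or a topical does not inform that comparison. Yet no section makes such treatment a non-response, and 12.4.3 as written accepts the cleared plaque.

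Treatment is open to subjects and investigators (Section 6.4), so use of other treatment may differ by arm. Blinded TCS scoring does not protect against this, because the plaque really is clear. Extra clearances among guselkumab non-responders hide a real difference; among secukinumab non-responders they can create a false one. With 20 subjects per arm, a few cases matter.

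**Working it through.** **Inputs.** 20 subjects per arm, one-sided Fisher's exact test at 0.05, assumed response rates of 75% (secukinumab) and 35% (guselkumab), all from Sections 12.4.2 and 12.9.1. The protocol gives no rate of discontinuation or of prohibited treatment, so every frequency below is an assumption.

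**Method.** P-values are hypergeometric tail probabilities for the 2×2 table. Power is the sum, over all 21 × 21 outcomes with p ≤ 0.05, of Bin(a; 20, P1) × Bin(b; 20, P2).

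**The plan's own figure.** P1 = 0.75, P2 = 0.35 gives 72.4%, which agrees with the 72% in Table 12-1.

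**Time for another treatment to act.** For a subject who stops drug but is scored at Week 16: 16 − 4 = 12, 16 − 8 = 8 or 16 − 12 = 4 weeks after stopping at Week 4, 8 or 12. If the visit is held at discontinuation, there is little time.

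**Effect on the planned result.** Expected counts are 20 × 0.75 = 15 and 20 × 0.35 = 7. Each added subject is assumed to be a non-responder otherwise.

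| Subjects cleared by other treatment | Responders | One-sided p |
|---|---|---|
| none | 15 v 7 | 0.0124 |
| 1 guselkumab | 15 v 8 | 0.0268 |
| 2 guselkumab | 15 v 9 | 0.0527 |
| 1 in each arm | 16 v 8 | 0.0112 |
| 2 in each arm | 17 v 9 | 0.0094 |

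In the other direction, one secukinumab subject matters only near the boundary: 13 v 7 (p = 0.0564) becomes 14 v 7 (p = 0.0281).

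**Effect on power.**

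- Guselkumab only, on average 1 of 20 (P2 = 0.35 + 0.05 = 0.40): 61.0%. On average 2 of 20 (P2 = 0.45): 49.1%.
- A share f of non-responders in both arms, P1 = 0.75 + 0.25f and P2 = 0.35 + 0.65f: f = 0.10 (0.775 v 0.415) gives 65.0%; f = 0.20 (0.80 v 0.48) gives 57.9%. Equal use costs power because 13 guselkumab but only 5 secukinumab non-responders are expected.

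**Effect on false positives.** With both true rates at 0.50 the rejection rate is 2.13%. If 10% or 20% of secukinumab non-responders only are cleared (0.55 or 0.60 v 0.50), it is 4.36% or 8.32%. If the same shares of guselkumab non-responders only are cleared (0.50 v 0.55 or 0.60), it is 0.97% or 0.41%. Only the 8.32% case exceeds 5%.

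**The case against.** **The carried-forward wording suggests an early visit.** A TCS taken at Week 16 needs no carrying forward, and Section 8 sends study leavers to a prompt final visit. On that reading another treatment has little time to act. This is a fair reading and shrinks the problem. It does not settle it: Section 9.1.1 keeps a subject who stops drug in the study and points to a schedule whose next visit is Week 16, and 12.4.3 does not distinguish the two groups.

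**A breach need not lead to discontinuation.** Footnote a of Table 6-2 makes stopping largely a matter of discretion where there is undue safety risk; only a live virus vaccination in a secukinumab subject compels it. This stands. A subject who breaches and stays on drug falls under the general definition in 12.4.2, which an SAP could refine.

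**The as-observed analysis may remove these subjects.** A reader might infer that they always remain responders there, because a Week 16 TCS is observed. The text does not support that as a certainty: 12.4.4 refers to the handling in 12.4.3 as imputation, so discontinuers' values may be dropped. But that would drop discontinuers whether or not they used other treatment, so the analysis still does not isolate the problem.

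**Attribution is not clean.** Guselkumab is given at Baseline, Week 4 and Week 12. A subject who stops after the Week 4 dose misses none until Week 12, so later clearance may partly reflect study drug. This also stands.

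**Scoring the outcome regardless of other treatment is legitimate.** The FAS follows the intent-to-treat principle, and such a policy can be defended. The protocol does not state that choice, however, and it fits poorly with an endpoint tied to treatment with the named drugs and with automatic failure before Week 4.

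**Conclusion.** The point holds as a weakness in a stated rule, of modest and unknown size. Section 12.4.3 lets a plaque cleared by a prohibited treatment count as a response to the assigned drug, and the protocol leaves open whether the exposure window is a few days or up to 12 weeks.

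A reader might infer that the planned result would be undone. The document does not support that. It takes two guselkumab subjects who each discontinue at Week 4 or later, use a barred treatment, clear to TCS 0-2 and would otherwise have failed, with no such subject on secukinumab; p then reaches 0.053, just over the threshold. With one or two in each arm, p is 0.011 or 0.009, slightly below the planned 0.012. At equal use per non-responder the rule works mainly against the superiority claim; one-sided use among secukinumab subjects would favour it. This is an optional improvement, worthwhile because it is cheap and brings the scoring into line with the endpoint definition.

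**What to change.** In Section 12.4.3, count as a non-responder any subject who, after first dose and before the End-of-study TCS, used a systemic psoriasis treatment or phototherapy prohibited by Section 6.2.2. Treat a prohibited topical the same way if the record shows, or cannot exclude, use on the target plaque. Identify these subjects from the concomitant-medication eCRF against a list fixed before database lock, by staff unaware of arm where feasible. In Section 12.4.4, report beside it the analysis of observed TCS regardless of such use.

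**Cost.** One sentence and one added analysis, with no new visits. Concomitant treatment is already recorded (6.2.1), also after study drug is stopped (9.1.1). The protocol does not say that the site of topical application is recorded, hence the default above; recording it would be a small addition.

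**Downsides.** If a share f of would-be responders in both arms is failed, the rates become 0.75(1 − f) and 0.35(1 − f). Power falls from 72.4% to 66.6% at f = 0.05 (0.7125 v 0.3325) and 61.3% at f = 0.10 (0.675 v 0.315). Arm-aware prescribing could also create failures: with both true rates at 0.50, failing 10% or 20% of guselkumab responders only (0.50 v 0.45 or 0.40) raises the false-positive rate from 2.13% to 4.36% or 8.32%. A gap between the two paired analyses would help to show either distortion.

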12.4.4 Sensitivity and supportive analyses

Analysis of the primary endpoint as observed i.e., without missing data imputation (as described in [Section 12.4.3](#)) will be performed as a sensitivity analysis for the primary endpoint.

12.5 Analysis of secondary endpoints

Not applicable.

12.6 Analysis of exploratory endpoints

The following exploratory endpoints will be analyzed:

- [REDACTED]
2. Change from Baseline to Week 16 in epidermal thickness and in the number of Ki-67 and K16 positive cells of lesional skin biopsies and difference from the Baseline non-lesional skin biopsy ([Section 8.3.4](#)) will be provided based on the FAS. Box plots and bar plots will also be provided
 3. Change from Baseline to Week 16 in the number of infiltrating cells expressing IL 17A and IL-23R of lesional skin biopsies and difference from the Baseline non-lesional skin biopsy ([Section 8.3.5](#)) will be provided based on the FAS
 4. Change from Baseline to Week 16 in the number of different immune cell types in the inflammatory infiltrate of lesional skin biopsies and difference from the Baseline non-lesional skin biopsy ([Section 8.3.6](#)) will be provided based on the FAS
- [REDACTED]
- [REDACTED]

[REDACTED]

[REDACTED] Values below the lower limit of quantification and above the upper limit of quantification will be flagged.

12.7 Safety analysis

The Safety Set will be used for all safety analyses. All summary tables and listings will be presented by treatment arm.

Safety summary tables will include only data from the on-treatment period (from first administration of study treatment to 30 days after the last administration of study treatment) with the exception of baseline data which will also be summarized where appropriate.

Adverse events

All information obtained on AEs will be displayed by treatment arm.

Summary tables for AEs will include only AEs that started or worsened during the on-treatment period, the *treatment-emergent* AEs (TEAEs).

The incidence of TEAEs will be summarized by system organ class and/or preferred term, severity based on the Common Terminology Criteria of Adverse Events (CTCAE) grades, type of AE and relation to study treatment.

Serious adverse events, AEs leading to discontinuation, and AEs leading to dose adjustment during the on-treatment period will be tabulated.

All on-treatment deaths will be summarized.

All AEs and SAEs will be listed.

A subject with multiple AEs within a primary SOC will only be counted once towards the total of the primary SOC.

[REDACTED]

Clinical laboratory evaluations

Grading of laboratory values will be assigned programmatically as per the CTCAE version 4.03. The calculation of CTCAE grades will be based on the observed laboratory values only, clinical assessments will not be taken into account.

CTCAE Grade 0 will be assigned for all non-missing values not graded as 1 or higher. Grade 5 will not be used. For laboratory tests where grades are not defined by CTCAE version 4.03, results will be categorized as low/normal/high based on laboratory normal ranges.

The following summaries will be generated separately for key hematology and biochemistry laboratory tests:

- shift tables comparing baseline to the worst on-treatment value. Each subject will be counted only once for the worst grade observed post-baseline.
- for laboratory tests where grades are not defined shift tables using the low/normal/high/ (low and high) classification to compare baseline to the worst on-treatment value will be used.

In addition to the above-mentioned tables and listings, other exploratory analyses, for example summary tables, figures plotting time course of raw or change in laboratory tests over time or box plots might be specified in the Statistical Analysis Plan. Listings will be provided for all data.

Other safety evaluations

Data on ECG, vital sign, height, and weight will be summarized descriptively, listed and flagged as appropriate. Any significant findings will be documented as AEs and reported as such.

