6.7.2 Instruction for prescribing and taking study treatment

Study treatments will be administered subcutaneously throughout the study (Table 6-3). The first dose will be administered under supervision at the study site. Self-administration at home will be allowed from the second dose or when the subject, after being instructed and trained, is qualified to self-inject at the discretion of the Investigator.

Study treatments must be injected in never-lesional areas of the skin to one of the following body regions: front of thighs, or lower abdomen (but not the area 2 centimeters around the navel). Investigator/qualified site staff can also inject in the outer upper arms. Study treatment should not be injected into areas where the skin is tender, bruised, red, scaly or hard, and areas with scars or stretch marks should be avoided. As far as possible, the injection site should be changed from administration to administration throughout the study.

Detailed instructions on the self-administration of the study treatment will be described in the instructions for use and provided to each subject.

Subjects will be asked to return all used and unused medication and packaging at each scheduled study visit.

Secukinumab 300 mg s.c.

Secukinumab will be administered at Baseline, Weeks 1, 2, 3, 4 and then every 4 weeks until Week 12 inclusive. After Week 4 (the last weekly administration of secukinumab), the subjects will be contacted by the Investigator or staff and be reminded to start the self-administration every 4 weeks instead of every week until Week 12.

Guselkumab 100 mg s.c.

Guselkumab will be administered subcutaneously at Baseline, Weeks 4, and 12.

Table 6-3 Study treatment administration schedule

Treatment	Baseline	Week 1	Week 2	Week 3	Week 4	Week 8	Week 12
Secukinumab	X	X	X	X	X	X	X
Guselkumab	X				X		X

7 Informed consent procedures

Eligible subjects may only be included in the study after providing (witnessed, where required by law or regulation), Institutional Review Board/Independent Ethics Committee (IRB/IEC)-approved informed consent.

If applicable, in cases where the subject's representative gives consent (if allowed according to local requirements), the subjects must be informed about the study to the extent possible given their understanding. If the subjects are capable of doing so, they must indicate agreement by personally signing and dating the written informed consent document.

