9.2 Study completion and post-study treatment

Study completion is defined as when the last subject finishes their End-of-study Visit, and any repeat assessments associated with this visit have been documented and followed up appropriately by the Investigator, or in the event of an early study termination decision, the date of that decision (e.g., each subject will be required to complete the study in its entirety and thereafter no further study treatment will be made available to them).

All randomized and/or treated subjects should have a safety follow up conducted 30 days after the last administration of study treatment. This will be performed at Week 16 for subjects who complete the study [last administration received at Week 12]. The information collected is kept as source documentation. All SAEs reported during this period must be reported as described in [Section 10.1.3](#). Attempts to contact the subject should be recorded in the source documentation.

10 Safety monitoring and reporting

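### The 30-day on-treatment window covers every secukinumab dosing interval but leaves 25 days of guselkumab's 8-week interval out of the safety tables for subjects who stop before Week 12

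*Protocol*

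**What the plan says.** Section 12.7 defines the on-treatment period once, for both arms: "Safety summary tables will include only data from the on-treatment period (from first administration of study treatment to 30 days after the last administration". Baseline data are the only stated exception.

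The same section applies the period table by table:
- AEs: "Summary tables for AEs will include only AEs that started or worsened during the on-treatment period".
- The more serious categories: "Serious adverse events, AEs leading to discontinuation, and AEs leading to dose adjustment during the on-treatment period will be tabulated".
- Laboratory data: "shift tables comparing baseline to the worst on-treatment value".

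The listings are not restricted: "All AEs and SAEs will be listed".

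Section 6.7.2 gives the two schedules: "Secukinumab will be administered at Baseline, Weeks 1, 2, 3, 4 and then every 4 weeks until Week 12 inclusive", and "Guselkumab will be administered subcutaneously at Baseline, Weeks 4, and 12". Table 8-1 schedules laboratory samples only at Screening and End of study, so each subject has one scheduled post-baseline sample. Section 8 asks for the final visit promptly after early discontinuation. The protocol has no arm-specific window, and no rule that keeps later events or samples in the tables.

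**The concern.** A window of fixed length after the last dose treats two arms alike only if it is at least as long as the dosing interval in each. Here it is longer than every interval in one arm and much shorter than one interval in the other. A guselkumab subject can be fully on schedule, waiting for the Week 12 dose, and already count as off treatment if that dose is never given.

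The subjects affected are those who stop between the Week 4 and Week 12 doses, and a table of AEs leading to discontinuation exists to describe such subjects. Any error goes one way: it lowers the tabulated guselkumab incidence relative to secukinumab. In an open-label study run by the sponsor of secukinumab, a rule that can undercount only the comparator is best removed in advance.

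**Working it through.** The protocol gives no coverage figure to reproduce, so the check is calendar arithmetic on its own schedule.

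**Inputs.** The window ends at last dose + 30 days (Section 12.7). Dose weeks are in Section 6.7.2 and Table 6-3. The End-of-study Visit is on Day 112 ± 2 days (Table 8-1). There are 20 subjects per arm (Section 12.9.1).

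**Formula.** Take Baseline as Day 1, so Week *w* is Day 7*w* + 1. For a subject whose last dose was on day *d*, with the next dose due on day *n*:

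uncovered days = max(0, (*n* − 1) − (*d* + 30))

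| Arm | Last dose | Covered to | Next dose due | Uncovered days |
|---|---|---|---|---|
| Secukinumab | Weeks 0, 1, 2, 3 (Days 1, 8, 15, 22) | Days 31, 38, 45, 52 | Days 8, 15, 22, 29 | 0 |
| Secukinumab | Week 4 (Day 29) | Day 59 | Day 57 | 0 |
| Secukinumab | Week 8 (Day 57) | Day 87 | Day 85 | 0 |
| Guselkumab | Week 0 (Day 1) | Day 31 | Day 29 | 0 |
| Guselkumab | Week 4 (Day 29) | Day 59 | Day 85 | 84 − 59 = **25** (Days 60–84) |
| Both | Week 12 (Day 85) | Day 115 | none; visit window Days 110–114 | 0 |

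The gap is 25/56 = 45% of the guselkumab interval, and 0% of any secukinumab interval.

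**Day convention.** Table 8-1 puts Week 16 at Day 112, which implies Week *w* = Day 7*w*. Week 4 is then Day 28, coverage ends on Day 58, the next dose is due on Day 84, and Days 59–83 are uncovered. That is again 25 days, and secukinumab again has none.

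**Worked case.** An event starts on Day 70 and the subject stops because of it.
- Guselkumab: the last dose was Day 29, and 70 − 29 = 41 days, which exceeds 30. The event is not treatment-emergent and is not in the discontinuation table. The final visit cannot be before Day 70, so the one scheduled post-baseline laboratory sample is outside the window even if the visit is the same day.
- Secukinumab: the last dose was Day 57, and 70 − 57 = 13 days. The event is counted, and so is a laboratory sample taken by Day 87.

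**Size.** Each omitted subject is 1/20 = 5 percentage points of the arm. The protocol gives no discontinuation rate. Purely as an assumption, suppose 5% to 20% of 20 subjects (1 to 4) stop, evenly over 112 days. The expected number stopping within the gap is then 1 × 25/112 = 0.2 to 4 × 25/112 = 0.9. Those stopping because of a new event would be fewer.

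**Check of the fix.** With the period ending at max(last dose + 30, next planned dose), the guselkumab Week 4 row becomes max(59, 85) = Day 85, with 0 uncovered days. Every other row is unchanged, because the 30-day limit is already the later date or no further dose is planned.

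**The case against.** The strongest reply is that this is a rare path with little consequence. Much of that stands.

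- The window runs without a break from first dose to 30 days after the last. A guselkumab subject who receives the Week 12 dose therefore has no gap between Weeks 4 and 12. A reader might infer from the 45% that nearly half of guselkumab safety time in that interval is lost. The documents do not support this: 45% is a share of calendar days for subjects who stop in the interval, not of subjects or events. An event that starts by Day 59 and later leads to discontinuation is still treatment-emergent.
- The data are not lost. All AEs and SAEs are listed, and with 20 subjects per arm a reader can find them. Section 12.7 plans descriptive summaries, with no test between arms. But a listing gives no incidence by arm, and the tables are what readers compare.
- A reader might infer that completers also lose their Week 16 laboratory sample. Section 9.2 says of the safety follow-up: "This will be performed at Week 16 for subjects who complete the study". An on-time Week 12 dose is covered to Day 115 (Day 114 on the other day convention), and the visit window ends on Day 114, so no on-schedule completer is dropped. An early home dose could change that, but as a deviation possible in either arm.
- The laboratory wording is mixed. The shift-table item refers to the worst on-treatment value and then to the worst grade after baseline. The restriction to the on-treatment period is still the general rule of the section. A much delayed final visit could also exclude a secukinumab sample; in the guselkumab gap, even a same-day visit does.
- The 30-day limit matches safety collection in Table 8-1 note 3 and Sections 9.2, 10.1.1 and 10.1.3. This bears on how the fix is made.

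**Conclusion.** The point holds in limited form. The rule in Section 12.7 creates an uncovered period of 25 of 56 days for guselkumab subjects who stop between the Week 4 and Week 12 doses, and none for on-schedule secukinumab subjects. Within it, the event that led to stopping is left out of the TEAE and discontinuation tables (and the SAE table if serious), and the subject's only scheduled post-baseline laboratory sample falls outside the on-treatment shift table.

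The 25 days rest on doses given on schedule and do not depend on the day convention. How many subjects are affected cannot be computed from the protocol. It is probably few, and below one under the assumed rates above, but each is worth 5 percentage points of the arm. The direction is fixed: the guselkumab tables can only be too low. The change is worth making before data are seen because the rule is written into the protocol and is simple to correct.

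**What to change.** In Section 12.7, for both arms, define the on-treatment period as first dose through the later of 30 days after the last dose and the date the next dose was planned. Use it for the AE and laboratory tables. Keep the early-termination laboratory sample in the shift table when that visit falls in the period. After the Week 12 dose no further dose is planned, so the 30-day limit applies as now.

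Do not extend the period to the End-of-study Visit whatever its timing. Section 9.1.1 lets discontinued subjects return on the visit schedule. A subject whose last dose was at Week 4 and who is seen on Day 112 would add 112 − 59 = 53 days beyond the 30-day limit (54 on the other convention), possibly on new treatment.

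The cost is one definition and its programming, with no change to dosing or clinical management. A few later events will be counted. SAE collection should be aligned with the same period: Table 8-1 note 3 ends it at 30 days, and Section 10.1.3 asks for later SAEs only when a causal relationship is suspected. Without that, the added days would have weaker SAE capture. Sections 9.1.1 and 10.1.1 already provide for AE collection after treatment stops, with 30 days as a minimum, so the alignment is small.
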